- Abdoli et al. [2018]³⁵ describe the performance of Artegraft implants that were cannulated early (<3 days) after implantation and associated clinical outcomes in 63 consecutive dialysis-dependent patients. 31 (49%) patients were cannulated early, and of the 31 patients cannulated early, 21 (68%) were cannulated during the first postoperative day. Early complications, primary patency, secondary patency, and tunneled dialysis catheter [TDC] incidence were monitored through clinic visits, hospital records, and survey calls to dialysis centers. The primary patency of the grafts at 1 year was 28% and 39% and secondary patency at 1 year was 74% and 77%, in the early and late cannulation cohorts, respectively. Early complications occurred in 11 (19%) patients who received an Artegraft and there were no significant differences in complication rates between early and late cannulation patients. Of the 24 patients who underwent the operation without a pre-existing TDC, only three (13%) required TDC placement during the 30-day postoperative period. These data led the authors to conclude that Artegraft implants can be cannulated early without increased complication rates or a negative impact on midterm patency and can minimize the need for a TDC postoperatively in dialysis-dependent patients undergoing primary vascular access or fistula revision procedures.

Artegraft, Inc.
Protocol: ARTCT.BEACH.001

In conclusion, Artegraft has presented existing clinical data that supports early access of hemodialysis grafts and proposes a prospective study in addition to the existing clinical data and literature to support labeling for early access.

Patency

The patency data reported in all the articles reviewed for this protocol support few, if any, conclusions. Six articles were found in which Artegraft and an ePTFE graft were compared; five articles described only the performance of the Artegraft. Two articles concluded that patency rates were superior for ePTFE,^{27,28} two for Artegraft^{14,15} and two showed no significant difference^{29,30}. Patency data reported in the literature for Artegraft are summarized (Table 3).

Since there have been changes in clinical practice over the 45 years that this graft has been marketed in the U.S., the more current articles may be weighted more highly.

Table 4: Reported Patency Data for Artegraft

| Performance Parameter | Mean | Min | Max | | | |
|------------------------------|------|-----|-----|--|--|--|

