Artegraft will follow all study patients enrolled in the proposed clinical trial and that have successful cannulation within 72 hours as defined above, for 6 months. If follow-up is necessary at 1 year after graft implantation, it will be done via phone survey. The late-access group [>/= 10 days] will be followed to 30 days post-first cannulation. Day 0 is defined as the day of first cannulation, for early-access and late-access groups, to allow full follow-up to at least 30 days for both groups

Artegraft, Inc. Version 4.0 21June2019
Protocol: ARTCT.BEACH.001 CONFIDENTIAL Page 26 of 81

Table 5: Risk Analysis Associated with Early Access

| Risk | Timing of Potential Risk | Rating of Risk ¹ | Non- Clinical Testing ² | Relevant Clinical Endpoint |
|---|--|--------------------------------|--|---|
| Serious Graft Infection | Typically, between 0 (surgical or device) and 180 days (cannulation) | 3 | none | Requires Intervention |
| Serious Hemorrhage / Hematoma | Between initial cannulation and 10 days | 3 | none | Requires Intervention |
| Excessive needle hole bleeding ³ | After removal of each cannula | 1 | none | Requires Additional Direct Pressure Time |
| Occlusion; primary and secondary | Ongoing with A/V access | 3 | none | Requires Intervention ⁴ |
| Inability to Cannulate | Immediate and up to 10 days | 2 | none | Continual or need for dialysis catheter |

¹ Rating: 1=Minimal; 2=Mild; 3=Serious; 4=Life-threatening; 5=Death

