4.0 OBJECTIVES AND ENDPOINTS

Table 6: Study Objectives and Endpoints

| able 0. Study Objectives and Endpoints | | | | |
|---|---|--|--|--|
| Study Objective | The objective of the BEACH Trial is to demonstrate that early access of Artegraft is associated with acceptable rates of successful early access, and acceptable rates of a composite of adverse events, to support a modification of existing device labeling stating that Artegraft is capable of cannulation within 72 hours post implantation. | | | |
| Primary Effectiveness Endpoint | Early access success, defined by three cannulations, the first one started within 72 hours post implantation, all with minimum dialysis flow rates of 250 ml/min pump flow rate, with a minimum 17-guage needle. | | | |
| | Expectations: $^{\sim}80\%$ of patients in the early access group will have first cannulation within 72 hours. | | | |
| | Expectations: ~90% of patients receiving early access will have 3 successful cannulations. | | | |
| Primary Safety Endpoint | A composite of major adverse clinical events (MACE) including perigraft infection, hemorrhage, thrombosis, steal syndrome, and pseudoaneurysm within 30 days after first cannulation [Day 0] in the early-access and late-access groups. | | | |
| | Expectation: ~20% of patients will have at least one MACE event; no significant difference in event number or type between early and late access groups. | | | |
| | All MACE will be adjudicated by an independent accessor. | | | |
| Secondary Effectiveness Endpoints | Patency (Primary, Assisted Primary, and Secondary) at 30 days after first successful cannulation [Day 0], and at 12 weeks and 6 months after implantation in the early-access group and at 30 days post-Day 0 in the lateaccess group. The late access group will also be assessed for patency at 6 months through a telephone interview or office visit to provide a more robust data set. | | | |
| | Expectations: | | | |
| | Patency rates [all 3 types] at 30 days will be similar in the early and late access groups. | | | |
| | We expect primary patency to be ≥85%, ≥75% and ≥65% at 30 days, 3 months, and 6 months, respectively. | | | |
| | Primary-assisted patency rates at 30 days, 3 months, and 6 months will be ≥85%. | | | |
| | Secondary patency rates will be ≥90% and ≥90% at 3 and 6 months, respectively. | | | |

Artegraft, Inc.
Protocol: ARTCT.BEACH.001

Version 4.0 CONFIDENTIAL 21June2019 Page 29 of 81

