9.2.4 Patient Populations for Analysis

Five analysis populations will be defined for use with various analyses. The following table illustrates the relationship between each population and the analyses for which the data from the population will be used.

Table 8: Patient Population for Analysis

| | Analysis | | | | |
|-----------------------|----------|---------------------|-------------------------------|--------|-------------|
| Analysis Population | Baseline | Patient Disposition | Effectiveness/ Performance | Safety | Product Use |
| Screened | | x | | | |
| Intent-to-treat (ITT) | х | x | | | |
| Safety | | | | Х | х |
| Effectiveness | | | Х | | |
| Per-protocol | | | Χ [†] | | |

[†] Analysis done only if any data from more than 5% of effectiveness analysis population patients are excluded from this population.

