10.1 Safety Assessments

10.2 Adverse Events

The definitions of SAE can be found in Appendix 4.

Adverse events will be reported by the patient (or, when appropriate, by a caregiver, surrogate, or the participant's legally authorized representative) or may be obtained from the patient's dialysis center.

The Investigator and any designees are responsible for detecting, documenting, and recording events that meet the definition of an AE or SAE and remain responsible for following up AEs that are serious, considered related to the study device or study procedures, or that caused the subject to discontinue the Artegraft device(see Section 8.0 Study Procedures).

Expected Adverse Events

Table 9: Expected Procedure-Related Adverse Events

| Bleeding |
|--|
| Death |
| Disruption or tearing of the suture line, graft, or host vessel |
| Embolism |
| Graft redundancy |
| Intervention complication (e.g., venous rupture) |
| Occlusion |
| Pain |
| Thrombosis |
| Technical complications (anastomosed to diseased vessel; graft physically compressed; incorrect sizing; implant technique; radiology infiltrated graft; bleeding from native vessel) |

Artegraft, Inc. Version 4.0 21June2019
Protocol: ARTCT.BEACH.001 CONFIDENTIAL Page 47 of 81

Table 10: Expected Device-Related Adverse Events

| Access failure; loss of access |
|--|
| Aneurysm |
| Bleeding |
| Cannulation-associated complication / trauma |
| Death |
| Embolic event |
| Graft dilatation |
| Hand ischemia, acute |
| Hand ischemia, subacute (delayed but w/in 1 month of implant) |
| Hematoma |
| Hemorrhage |
| Infection (cellulitis, abscess, septic emboli, bacteremia, sepsis) |
| Intervention (surgical, angioplasty, stenting, thrombectomy, thrombolysis, revision) |
| Inflammation / sensitivity to device materials |
| Invasive surgical procedure |
| Kinking |
| Low flow |
| Neointimal hyperplasia |
| Pain |
| Primary graft failure |
| Pseudoaneurysm |
| Seroma |
| Skin erosion; lesion |
| Slow wound healing |
| Steal syndrome |
| Stenosis |
| Swelling of the implanted limb |
| Thrombosis / occlusion, graft |
| Thrombosis, other |
| Ultrafiltration |

All AEs will be collected from the start of treatment until the final follow-up visit at the time points specified in the SoA's (Table 1a and Table 1b).

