10.2.6 Stopping Rules

The FDA cleared this device and it has been on the market for more than 40 years. Justifications of the following stopping rules are based on previously published safety data for Artegraft.

Stopping Rules include:

- MACE in more than 20% of early-access patients within 30 days of Day 0
- MACE not listed in Table 4 in early-access patients
- Any SAE not listed in Tables 8 and 9 in early-access patients

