Appendix 3 - Clinical Laboratory Tests

The tests detailed in **Table 11** may be performed at any time during the study as determined necessary by the Investigator or required by local regulations.

Table 12: Protocol-required Laboratory Assessments

| Laboratory Assessments | Parameters |
|---|--|
| Hematology | Prothrombin Time INR (coagulation) Platelet Count Red Blood Cell (RBC) Count Hemoglobin Hematocrit RBC Indices: Mean corpuscular volume (MCV) Mean corpuscular hemoglobin (MCH) %Reticulocytes White Blood Cell Count with Differential: Neutrophils Lymphocytes Monocytes Eosinophils Basophils |
| Clinical Chemistry | Blood Urea Nitrogen Creatinine Sodium Potassium Hemoglobin A1C Alkaline phosphatase Total Protein Glucose; non-fasting ALT AST Total Bilirubin |
| Other Screening Tests | Human chorionic gonadotropin (hCG) serum pregnancy test (for women of childbearing potential) |
| The results of each test must be entered into the (e)CRF. | |

Appendix 4 - Adverse Events: Definitions and Procedures for Recording, Evaluating, Follow-up, and Reporting

Definition of AEs for Medical Devices

Adverse Device Effect

An AE related to the use of an investigational medical device is classified as an adverse device effect (ADE).

Note 1: This definition includes AEs resulting from insufficient or inadequate IFU, deployment, implantation, installation, operation, or any device malfunction of the investigational medical device. This definition includes any event resulting from the use error or intentional misuse of the investigational medical device.

Adverse Event

Any untoward medical occurrence, unintended disease or injury or untoward clinical signs (including an abnormal laboratory finding) in patients, users or other persons whether or not related to the investigational medical device.

This includes events related to the investigational medical device or the comparator. This includes events related to the procedures involved. For users or other persons this is restricted to events related to the investigational medical device.

Serious Adverse Event / Serious Adverse Device Effect

An AE that:

led to a death,

led to a serious deterioration in the health of the patient user or other persons that either resulted in:

- 1) a life-threatening illness or injury, or
- 2) a permanent impairment of a body structure or a body function, or
- 3) in-patient or prolonged hospitalization, or

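### Two stopping triggers in section 10.2.6 conflict with the protocol's own definitions: one unrelated unlisted SAE, or one case of a pre-specified MACE component, is enough to meet a rule

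*Combined protocol and SAP*

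**What the plan says.** Section 10.2.6 gives three stopping rules for early-access patients. The first is a rate with a window: MACE in more than 20% of patients within 30 days of Day 0. The second is "MACE not listed in Table 4 in early-access patients". The third is "Any SAE not listed in Tables 8 and 9 in early-access patients". The section does not say what follows when a rule is met, or who decides. Section 10.3 plans no interim analysis.

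Appendix 4 defines an adverse event without regard to its relation to the device. An SAE is one that led to death or to a serious deterioration in health resulting in, among other things, "in-patient or prolonged hospitalization". The carve-out covers planned admissions for a pre-existing condition and protocol-required procedures, in both cases without serious deterioration. Appendix 4 also defines the unexpected serious adverse device effect, and section 10.4 has an independent assessor adjudicate SAEs possibly or definitely related to device or procedure. Section 10.2.6 refers to neither.

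Section 4.0 defines the primary safety composite as "perigraft infection, hemorrhage, thrombosis, steal syndrome, and pseudoaneurysm within 30 days" after first cannulation. Section 10.2.5 names the same five components. The synopsis list omits steal syndrome.

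**The concern.** The first rule is graded: it allows some MACE and reacts to an excess. The other two react to a single event and define that event by its absence from a list. Such a rule works only if the lists are complete for the events that should not trigger it.

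For SAEs, the expected-event lists cover the procedure and the access. An unplanned admission for, say, myocardial infarction or an electrolyte emergency is on neither list, whatever its connection with early cannulation. For MACE, the reference list is shorter than the endpoint's own definition. These are the only pre-specified safety thresholds in the protocol. If unrelated or anticipated events can meet them, they will tend to be set aside case by case, and they become weak evidence about the safety of early access.

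**Working it through.** **1. SAE trigger.** The protocol gives no probability of meeting this rule and no rate of unlisted SAEs, so there is no figure of its own to reproduce.

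Inputs: n = 50 early-access patients (section 9.1), with adverse events collected to 6 months in that group (synopsis, secondary safety endpoint). One qualifying event suffices (section 10.2.6). The per-patient risk p of at least one unlisted SAE over follow-up is my assumption, shown as a range.

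With independent patients and a common risk, P(rule met) = 1 − (1 − p)^50.

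| Assumed p | Calculation | P(rule met) |
|---|---|---|
| 0.5% | 1 − 0.995^50 | 22% |
| 1% | 1 − 0.99^50 | 39% |
| 2% | 1 − 0.98^50 | 64% |
| 5% | 1 − 0.95^50 | 92% |
| 10% | 1 − 0.90^50 | 99.5% |

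The probability reaches one half at p = 1 − 0.5^(1/50) = 1.38%, 80% at p = 3.2% and 90% at p = 4.5%.

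**2. MACE trigger.** Take the reference to mean the risk analysis table in section 3.3, which is the reading most favourable to the rule.

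| MACE component (section 4.0) | Row in the risk analysis table | In the device-related expected list (section 10.2) |
|---|---|---|
| Perigraft infection | Graft infection | Yes, as infection |
| Hemorrhage | Hemorrhage / hematoma | Yes |
| Thrombosis | Not by name; falls under occlusion | Yes |
| Steal syndrome | None | Yes |
| Pseudoaneurysm | None | Yes |

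The two remaining risk rows, needle-hole bleeding and inability to cannulate, cover neither missing component. One pseudoaneurysm or one steal syndrome therefore meets the second rule. The first rule tolerates MACE in 20% of 50 = 10 patients and is exceeded only at the 11th. The same event is also expected for the purposes of the third rule, so the second and third rules classify it in opposite ways.

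As an illustration of size, section 3.2 quotes an overall steal incidence of 4.7% from one retrospective comparison of bovine and PTFE grafts. If all of it fell within 30 days, P(at least one in 50) = 1 − 0.953^50 = 91%. If one half, one quarter or one tenth did, p is 2.35%, 1.175% or 0.47% and the probability is 70%, 45% or 21%. The fraction is assumed; the protocol does not give it.

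**3. Table numbering.** The List of Tables numbers the risk analysis as 4, the procedure-related expected events as 8 and the device-related ones as 9, which are the tables the rules need. In-text references follow the same numbering: milestones as Table 2 (section 2.2), patency as Table 3 (section 3.2), risk as Table 4 (section 3.3), laboratory tests as Table 11 (Appendix 3). The body captions run one higher: "Table 4: Reported Patency Data for Artegraft", "Table 5: Risk Analysis Associated with Early Access", "Table 8: Patient Population for Analysis" and "Table 10: Expected Device-Related Adverse Events". The shift begins where the second schedule of assessments, called Table 1b in section 10.2, is captioned 2b. Steps 1 and 2 do not depend on which numbering is used.

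**The case against.** Four arguments can be made on the other side.

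First, a reader going by the captions might infer that the rules point to the wrong tables, so that every MACE is unlisted and expected device events such as infection trigger the SAE rule. The documents do not support this. The pointers agree with the List of Tables and with the other in-text references; it is the captions that slipped. That part is editorial.

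Second, a reader might infer that any hospital admission counts. It does not: Appendix 4 requires serious deterioration and excludes certain planned or protocol-required admissions. The expected lists are also broad, including death, embolic events, sepsis, invasive surgery and pain, which shrinks the unlisted pool. This stands. It bears on the size of p, not on the absence of a relatedness limit.

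Third, a reader might infer that the rule is likely, or almost certain, to be met. The protocol supplies no rate, and at an assumed 1% the rule is met less often than not. What can be said is conditional: above about 1.4% it is more likely than not.

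Fourth, a reader might infer that the trial would stop automatically. Section 10.2.6 defines no action, and Appendix 4 only lets the assessor recommend modification or termination. The supportable statement is that the rule is met, not that the trial ends. The undefined action is a separate gap, and it does not repair the triggers.

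**Conclusion.** The point holds in two parts, under either table numbering. The SAE trigger takes no account of cause, count or time, so a single unrelated, unlisted SAE among 50 patients meets it. The chance is 39% to 99.5% for assumed per-patient risks of 1% to 10%, and exceeds one half above about 1.4%. These figures assume independent patients with a common risk, and the risk itself is not in the documents.

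The MACE trigger contradicts the endpoint definition: one pseudoaneurysm or steal syndrome meets it, while the first rule tolerates up to 10 patients with MACE in 50. This follows from the lists alone and needs no assumed rate. For steal syndrome the conflict also runs through the MACE lists themselves, since the synopsis omits it; pseudoaneurysm is in all three.

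As written, the rules give a wrong result. The documents do not show that the trial will probably stop, or that it would stop without a decision by someone.

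**What to change.** - Reconcile the MACE lists in the synopsis, section 4.0 and section 10.2.5 with one another and with the risk analysis table, so that a pre-specified component does not count as unlisted.
- Reconcile the SAE trigger with the relatedness adjudication in section 10.4 and the unexpected serious adverse device effect category in Appendix 4. The sponsor and the assessor should state the intended scope; no particular criterion is proposed here.
- Report the chance of meeting each trigger under stated event rates.
- Correct the body captions so that they agree with the List of Tables and the in-text references. Changing the pointers instead would break that agreement.

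The cost is wording, with no change to sample size, visits or data collection. If the scope is limited to related events, there is a downside: unrelated unlisted SAEs would go to the assessor for review rather than meet a rule.

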10.2.7 Medical Device Malfunctions

Medical devices are being provided for use in this study to define safety and performance of the Artegraft for early access. To fulfill regulatory reporting obligations worldwide, the Investigator is responsible for the detection and documentation of events meeting the definitions of incident or device malfunction that occur during the study with such devices. Device malfunctions expected for product code LXA (from the FDA TPLC database) are: leak (hole, break, material integrity such as to cause true or pseudo aneurysm) and compromised packaging.

The definition of a Medical Device Incident can be found in Appendix 5.

NOTE: Incidents fulfilling the definition of an AE/SAE will also follow the processes outlined in Section 10.2.2 and Appendix 4 of the protocol.

10.2.7.1 Period for Detecting Medical Device Malfunctions

- Medical device malfunctions or device malfunctions of the device that result in an incident will be detected, documented, and reported during all periods of the study in which the medical device is used.
- If the Investigator learns of any incident at any time after a patient has been discharged from the study, and such incident is considered reasonably related to a medical device provided for the study, the Investigator will promptly notify the Sponsor.

Artegraft, Inc. Version 4.0 21June2019
Protocol: ARTCT.BEACH.001 CONFIDENTIAL Page 50 of 81

The method of documenting Medical device malfunctions is provided in Appendix 5.

10.2.7.2 Follow-up of Medical Device Malfunctions

- All medical device malfunctions involving an AE will be followed and reported in the same manner as other AEs (see Section 10.2.2). This applies to all patients.
- The Investigator is responsible for ensuring that follow-up includes any supplemental investigations as indicated to elucidate the nature and causality of the incident.
- New or updated information will be recorded on the originally completed form with all changes signed and dated by the Investigator.

10.2.7.3 Prompt Reporting of Medical Device Malfunctions to Sponsor

- Medical device malfunctions will be reported to the Sponsor within 24 hours after the Investigator determines that the event meets the protocol definition of a medical device incident.
- The Issue Management Form will be sent to the Sponsor by email to [contact]. If email is unavailable, then the [contact] (for registering the incident) should be used.

10.2.7.4 Regulatory Reporting Requirements for Medical Device Malfunctions

- The Investigator will promptly report all incidents occurring with any medical device provided for use in the study for the Sponsor to fulfill the legal responsibility to notify appropriate regulatory authorities and other entities about certain safety information relating to medical devices being used in clinical studies.
- The Investigator, or responsible person according to local requirements (e.g., the head of the medical institution), will comply with the applicable local regulatory requirements relating to the reporting of incidents to the IRB.

